## 6.5 Dose escalation and dose modification

### 6.5.1 Dose modifications

The starting dose for erenumab is 70 mg/1 mL and matching placebo is 1 mL. Subjects will keep this dose throughout the study. Study treatment dose adjustments are not permitted. For subjects who are unable to tolerate the protocol-specified dosing scheme, dose interruptions of study treatment are permitted in order to keep the subject on study drug. These changes must be recorded on the appropriate CRF.

### 6.5.2 Follow-up for toxicities

#### 6.5.2.1 Follow up on potential drug-induced liver injury cases

Subjects with transaminase increase combined with TBIL increase may be indicative of potential DILI and should be considered as clinically important events.

The threshold for potential drug-induced liver injury (DILI) may depend on the subject's baseline AST/ALT and TBIL value; subjects meeting any of the following criteria will require further follow-up as outlined below:

- For subjects with normal ALT and AST and TBIL value at baseline: AST or ALT  $> 3.0 \times$  ULN combined with TBIL  $> 2.0 \times$  ULN
- For subjects with elevated AST or ALT or TBIL value at baseline: [AST or ALT  $> 2.0 \times$  baseline AND  $> 3.0 \times$  ULN] OR [AST or ALT  $> 8.0 \times$  ULN], combined with [TBIL  $> 2.0 \times$  baseline AND  $> 2.0 \times$  ULN]

Medical review needs to ensure that liver test elevations are not caused by cholestasis, defined as alkaline phosphatase (ALP) elevation  $> 2.0 \times$  ULN with R value  $< 2$  in subjects without bone metastasis, or elevation of ALP liver fraction in subjects with bone metastasis.

Note: The R value is calculated by dividing the ALT by the ALP, using multiples of the ULN for both values. It denotes whether the relative pattern of ALT and/or ALP elevation is due to cholestatic ( $R \leq 2$ ), hepatocellular ( $R \geq 5$ ), or mixed ( $R > 2$  and  $< 5$ ) liver injury.

In the absence of cholestasis, these subjects should be immediately discontinued from study treatment, and repeat Liver Function Test (LFT) testing as soon as possible, preferably within 48 hours from the awareness of the abnormal results. The evaluation should include laboratory tests, detailed history, physical assessment and the possibility of liver metastasis or new liver lesions, obstructions/compressions, etc.

1. Laboratory tests should include ALT, AST, albumin, creatine kinase, total bilirubin, direct and indirect bilirubin, Gamma-glutamyl transferase (GGT), prothrombin time (PT)/ International Normalized Ratio (INR), and alkaline phosphatase.
2. A detailed history, including relevant information, such as review of ethanol, concomitant medications, herbal remedies, supplement consumption, and history of any pre-existing liver conditions or risk factors, should be collected.
3. Further testing for acute hepatitis A, B, C or E infection and liver imaging (e.g. biliary tract) may be warranted.
4. Obtain PK sample, as close as possible to last dose of, if PK analysis is performed in the study.
5. Additional testing for other hepatotropic viral infection (CMV, EBV or HSV), autoimmune hepatitis or liver biopsy may be considered as clinically indicated or after consultation with specialist/hepatologist.

All cases confirmed on repeat testing meeting the laboratory criteria defined above, with no other alternative cause for LFT abnormalities identified should be considered as “medically significant” and thus, meet the definition of Serious Adverse Event (SAE) and should be reported as SAE using the term “potential drug-induced liver injury”. All events should be followed up with the outcome clearly documented.

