## 10.2      Additional Safety Monitoring

### 10.2.1    Liver safety monitoring

To ensure subject safety and enhance reliability in determining the hepatotoxic potential of an investigational drug, a standardized process for identification, monitoring and evaluation of liver events has to be followed.

The following two categories of abnormalities / adverse events have to be considered during the course of the study (irrespective of whether classified/reported as AE/SAE):

- Liver laboratory triggers, which will require repeated assessments of the abnormal laboratory parameter
- Liver events, which will require close observation, follow-up monitoring and completion of the standard AE CRF pages

Please refer to [Table 16-2](#) in [Section 16.2](#) for complete definitions of liver laboratory triggers and liver events.

Once a subject is exposed to study treatment, every liver event defined in [Table 16-2](#) should be followed up by the investigator or designated personnel at the trial site, as summarized below. Additional details on actions required in case of liver events are outlined in [Table 16-3](#). Repeat liver chemistry tests (i.e. ALT, AST, TBIL, PT/INR, ALP and GGT) to confirm elevation.

- These liver chemistry repeats will be performed using the central laboratory. If results will not be available from the central laboratory, then the repeats can also be performed at a local laboratory to monitor the safety of the subject. If a liver event is subsequently

reported, any local liver chemistry tests previously conducted that are associated with this event should have results reported on the unplanned local laboratory CRF (or liver CRF page).

- If the initial elevation is confirmed, close observation of the subject will be initiated, including consideration of treatment interruption if deemed appropriate.
- Discontinuation of the investigational drug (refer to the Discontinuation of study treatment section), if appropriate
- Hospitalization of the subject if appropriate
- Causality assessment of the liver event
- Thorough follow-up of the liver event should include
  - These investigations can include based on investigator's discretion: serology tests, imaging and pathology assessments, hepatologist's consultancy; obtaining more detailed history of symptoms and prior or concurrent diseases, history of concomitant drug use, exclusion of underlying liver disease

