**Table 16-3 Follow Up Requirements for Liver Events and Laboratory Triggers**

Criteria	Actions required	Follow-up monitoring
Potential Hy's Law case a	
 
• Discontinue the study treatment immediately
 
• Hospitalize, if clinically appropriate
 
• Establish causality
 
	ALT, AST, TBIL, Albumin, PT/INR, ALP and GGT until resolution c (frequency at investigator discretion)
ALT or AST		
$> 8 \times \text{ULN}$	
 
• Discontinue the study treatment immediately
 
• Hospitalize if clinically appropriate
 
• Establish causality
 
	ALT, AST, TBIL, Albumin, PT/INR, ALP and GGT until resolution c (frequency at investigator discretion)
$> 3 \times \text{ULN}$ and $\text{INR} > 1.5$	
 
• Discontinue the study treatment immediately
 
	ALT, AST, TBIL, Albumin, PT/INR, ALP and GGT until resolution c (frequency at investigator discretion)

Criteria	Actions required	Follow-up monitoring
> 5 to $\leq$ 8 $\times$ ULN	

• Hospitalize, if clinically appropriate

• Establish causality

• Repeat LFT within 48 hours

• If elevation persists, continue follow-up monitoring

• If elevation persists for more than 2 weeks, discontinue the study drug

• Establish causality

	ALT, AST, TBIL, Albumin, PT/INR, ALP and GGT until resolution c (frequency at investigator discretion)
> 3 $\times$ ULN accompanied by symptoms b	

• Discontinue the study treatment immediately

• Hospitalize if clinically appropriate

• Establish causality

• Complete liver CRF

	ALT, AST, TBIL, Albumin, PT/INR, ALP and GGT until resolution c (frequency at investigator discretion)
> 3 to $\leq$ 5 $\times$ ULN (subject is asymptomatic)	

• Repeat LFT within the next week

• If elevation is confirmed, initiate close observation of the subject

	Investigator discretion Monitor LFT within 1 to 4 weeks
ALP (isolated)		
> 2 $\times$ ULN (in the absence of known bone pathology)	

• Repeat LFT within 48 hours

• If elevation persists, establish causality

	Investigator discretion Monitor LFT within 1 to 4 weeks or at next visit

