TBIL (isolated)		
> 2 $\times$ ULN (in the absence of known Gilbert syndrome)	

• Repeat LFT within 48 hours

• If elevation persists, discontinue the study drug immediately

• Hospitalize if clinically appropriate

• Establish causality

	ALT, AST, TBIL, Albumin, PT/INR, ALP and GGT until resolution c (frequency at investigator discretion) Test for hemolysis (e.g. reticulocytes, haptoglobin, unconjugated [indirect] bilirubin)
> 1.5 to $\leq$ 2 $\times$ ULN (subject is asymptomatic)	

• Repeat LFT within the next week

• If elevation is confirmed, initiate close observation of the subject

	Investigator discretion Monitor LFT within 1 to 4 weeks or at next visit
Jaundice	

• Discontinue the study treatment immediately

	ALT, AST, TBIL, Albumin, PT/INR, ALP and GGT until

Criteria	Actions required	Follow-up monitoring
Any AE potentially indicative of a liver toxicity*	

• Hospitalize the subject

• Establish causality

• Consider study treatment interruption or discontinuation

• Hospitalization if clinically appropriate

• Establish causality

	resolution c (frequency at investigator discretion) Investigator discretion

aElevated ALT/AST > 3 × ULN and TBIL > 2 × ULN but without notable increase in ALP to > 2 × ULN

b(General) malaise, fatigue, abdominal pain, nausea, or vomiting, or rash with eosinophilia

cResolution is defined as an outcome of one of the following: (1) return to baseline values, (2) stable values at three subsequent monitoring visits at least 2 weeks apart, (3) remain at elevated level after a maximum of 6 months, (4) liver transplantation, and (5) death.

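### Protocol Section 6.5.2.1 and Tables 16-2/16-3 can give different stopping instructions for the same liver results, explicitly so when ALP exceeds 2 × ULN and R is 2 or more, and nothing says which prevails.

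*Protocol*

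**What the plan says.** **Protocol Section 6.5.2.1.** The threshold for potential drug-induced liver injury "may depend on the subject's baseline AST/ALT and TBIL value". With normal baseline values the criterion is ALT or AST above 3 × ULN with bilirubin (TBIL) above 2 × ULN. A second branch applies "For subjects with elevated AST or ALT or TBIL value at baseline". It requires ALT or AST above both 2 × baseline and 3 × ULN (or above 8 × ULN alone), together with TBIL above both 2 × baseline and 2 × ULN. "Medical review needs to ensure that liver test elevations are not caused by cholestasis", which the section defines as ALP above 2 × ULN with R below 2. The instruction is then: "In the absence of cholestasis, these subjects should be immediately discontinued from study treatment". The same section ties the SAE term for potential drug-induced liver injury to its own laboratory criteria.

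**Protocol Section 10.2.1.** This section applies Table 16-2 to all exposed subjects and adds: "Additional details on actions required in case of liver events are outlined in" Table 16-3. It does not mention Section 6.5.2.1.

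**Protocol Table 16-3.** Footnote a defines a potential Hy's Law case as "Elevated ALT/AST > 3 × ULN and TBIL > 2 × ULN but without notable increase in ALP to > 2 × ULN". The action is "Discontinue the study treatment immediately". The definition uses neither baseline nor R. Two other ALT/AST rows matter here:
- Above 5 and up to 8 × ULN: repeat the tests within 48 hours, and stop the drug if the elevation lasts more than 2 weeks.
- Above 3 and up to 5 × ULN without symptoms: repeat within a week, then observe closely. No stop is stated.

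The ALP and TBIL rows are labelled as isolated elevations. The ALT/AST rows are not.

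**The concern.** Two parts of the protocol govern stopping study drug for a combined transaminase and bilirubin rise. They differ in how they treat a raised ALP and in whether they refer to baseline. If one result calls for an immediate stop in one place and for retesting in the other, the action taken depends on which section the site consults. The difference is more than a delay, because the glossary makes discontinuation permanent. A subject whose values settle within 2 weeks need not be stopped under the ALT/AST rows of Table 16-3, but has already been stopped for good under Section 6.5.2.1.

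**Working it through.** No figure in the plan underlies this point, so there is nothing to reproduce. The two rules were applied to the same example results. All values are multiples of ULN. The examples assume no symptoms, no jaundice, INR not above 1.5, bilirubin mainly conjugated (a qualifier that appears only in Table 16-2) and no bone disease.

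**Formulas**
- R = ALT / ALP (Section 6.5.2.1).
- Elevated-baseline thresholds in Section 6.5.2.1: the larger of 3 and 2 × baseline for ALT/AST (or above 8 alone), and the larger of 2 and 2 × baseline for TBIL.
- Exclusion criterion 16 admits ALT/AST below 3 and TBIL below 2 at screening, so subjects with raised baseline values can enter.

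| Baseline | On treatment: ALT / TBIL / ALP | Check | Section 6.5.2.1 | Table 16-3 |
|---|---|---|---|---|
| Normal | 4 / 2.5 / 1 | ALP not above 2 | Stop at once | Stop at once |
| Normal | 6 / 2.5 / 2.5 | R = 6/2.5 = 2.4 | Stop at once | Retest in 48 hours; stop only after more than 2 weeks |
| Normal | 4.8 / 2.5 / 2.2 | R = 4.8/2.2 = 2.18 | Stop at once | Retest within a week; observe |
| Normal | 6 / 2.5 / 4 | R = 6/4 = 1.5 | Exempt as cholestasis | Retest in 48 hours; stop only after more than 2 weeks |
| ALT 2.5 | 4.5 / 2.5 / 1 | 4.5 is not above 2 × 2.5 = 5.0 | Not triggered | Stop at once |
| TBIL 1.5 | 4 / 2.5 / 1 | 2.5 is not above 2 × 1.5 = 3.0 | Not triggered | Stop at once |
| TBIL 1.2 | 6 / 3 / 1 | 3 is above 2 × 1.2 = 2.4 | Stop at once | Stop at once |

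**Where the rules agree.** With normal baseline and ALP not above 2, the cholestasis exemption cannot apply and the two criteria coincide. A grid of 4,500 combinations (ALT 3.1 to 8, TBIL 2.1 to 5, ALP 1, 1.5 or 2) gave a stop under both rules at every point.

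**Where they clash explicitly (rows 2 and 3).** Both rules start from ALT/AST above 3 with TBIL above 2. When ALP is above 2, Table 16-3 leaves the potential Hy's Law row, while Section 6.5.2.1 still stops treatment if R is 2 or more. R is built on ALT, so ALP above 2 with R of at least 2 implies ALT above 2 × 2 = 4. Above 8, Table 16-3 stops treatment on transaminases alone. The clash therefore covers ALT above 4 and up to 8, with ALP above 2 and up to ALT/2 (at most 8/2 = 4). If a site used the TBIL row despite its isolated label, that row also asks for a repeat test before stopping, so it would not restore an immediate stop.

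**Where only the triggers differ (rows 5 and 6).** If baseline values stay within the screening limits, the thresholds in Section 6.5.2.1 can rise to just under 2 × 3 = 6 for ALT/AST and 2 × 2 = 4 for TBIL. Below them Section 6.5.2.1 is silent, while Table 16-3 stops treatment when ALP is not above 2. Such a subject is stopped as a potential Hy's Law case but falls outside the laboratory criteria for the SAE term.

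**A smaller point.** Section 6.5.2.1 uses R below 2 in its cholestasis definition, but its note calls R of 2 or less cholestatic. The two differ only at exactly R = 2.

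**The case against.** The strongest reply is that the rules are additive: a subject who meets either is stopped. On that reading every example has one answer, and Protocol Section 9.1.1 also lets the investigator stop for laboratory abnormalities or an unfavourable risk/benefit balance. But the protocol nowhere says the rules are additive. On that reading the baseline adjustment in Section 6.5.2.1 would never change a stopping decision when ALP is not above 2 × ULN, because every case meeting it already meets the fixed thresholds. Investigator judgement permits a stop; it does not say which written rule governs.

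Several stronger readings are tempting, and the documents do not support them:
- **That the rules are opposite in general, or that Section 6.5.2.1 directs continued dosing with a raised baseline.** It does not. The section is simply not triggered, and Table 16-3 still applies.
- **That the SAE term has two competing definitions.** It is defined only in Section 6.5.2.1. The gap is that a Table 16-3 stop can fall outside it.
- **That subjects would routinely be dosed again at some sites.** Double-blind doses are given on Day 1 and at Weeks 4 and 8 (Section 6.7.2). Table 8-1 appears to place post-Day 1 double-blind chemistry at End of Treatment, in the same position as the serum pregnancy test that Section 8.4.3 puts there. The table is broken in extraction, so this is a reading of it.
- **That liver safety results would not be comparable.** SAP Section 2.7.3 summarises liver abnormalities by arm from laboratory values, and no comparison between sites is planned.

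The metastasis wording in Section 6.5.2.1 is inert, since exclusion criterion 13 removes most recent malignancy. These replies narrow the point but leave the clash at ALP above 2 × ULN with R of 2 or more.

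**Conclusion.** The concern holds in a limited form. For a combined rise with ALT above 4 and up to 8 × ULN, TBIL above 2 × ULN, ALP above 2 × ULN and R of 2 or more, Section 6.5.2.1 requires an immediate permanent stop. The ALT/AST rows of Table 16-3 require retesting first, with a stop after more than 2 weeks' persistence or with observation only. This assumes no symptoms, no jaundice and INR not above 1.5, any of which would bring a stop under Table 16-3 as well. The difference for raised baseline values is secondary: one rule is silent where the other stops treatment, and the SAE criterion does not follow the stop.

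The documents give no frequency for these patterns. They should be rare, and the example grid says nothing about how often they occur. On the reading of Table 8-1 above, the effect falls mainly on unscheduled tests and open-label dosing. It does not touch the primary efficacy analysis method. It still needs correcting, because a stopping rule followed as written should give one action for one result.

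**What to change.** The sponsor, with its hepatic safety experts, should reconcile Section 6.5.2.1 with Tables 16-2 and 16-3. Four items need one answer each:
- the criteria for a combined ALT/AST and TBIL rise, including whether the conjugated-bilirubin qualifier applies;
- whether subjects with raised baseline values are judged against baseline or ULN, and which measurement counts as baseline;
- the cholestasis exception;
- the R cut-off.

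The protocol should then state which rule governs (or that both apply), cross-reference it from Sections 6.5.2.1 and 10.2.1, and align the SAE criterion in Section 6.5.2.1 with it. No view is given here on which rule is right. The metastasis wording can be removed at the same time. The cost is protocol wording in one amendment and a letter to sites; no new procedures or subjects are needed.

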## **6.6 Additional treatment guidance**

### **6.6.1 Treatment compliance**

During both the double-blind treatment and the open-label treatment period, the study medication is administered by the investigator or designated study staff at each visit. This information should be captured in the source documents and the CRF at each visit. All study treatment administered must be recorded in the Drug Accountability Log. Information regarding treatment during the COVID-19 pandemic can be found in [Section 13.2](#).

Site staff will review eDiary compliance with the subject at each visit during the double-blind treatment period.

### **6.6.2 Emergency breaking of assigned treatment code**

Emergency code breaks must only be undertaken when it is required to in order to treat the subject safely. Most often, study treatment discontinuation and knowledge of the possible treatment assignments are sufficient to treat a study subject who presents with an emergency condition. Emergency treatment code breaks are performed using the IRT. When the investigator contacts the system to break a treatment code for a subject, he/she must provide the requested subject identifying information and confirm the necessity to break the treatment code for the subject. The investigator will then receive details of the investigational drug treatment for the specified subject and a fax or email confirming this information. The system will automatically inform the Novartis monitor for the site and the study team that the code has been broken.

It is the investigator's responsibility to ensure that there is a dependable procedure in place to allow access to the IRT/code break cards at any time in case of emergency. The investigator will provide:

- protocol number
- study drug name
- subject number

In addition, oral and written information to the subject must be provided on how to contact his/her backup in cases of emergency, or when he/she is unavailable, to ensure that un-blinding can be performed at any time.

### **6.7 Preparation and dispensation**

Each study site will be supplied with study drug in packaging as described under investigational and control drugs section.

A unique medication number is printed on the study medication label.

Investigator staff will identify the study medication kits to dispense to the subject by contacting the IRT and obtaining the medication number(s). The study medication has a 2-part label (base plus tear-off label), immediately before dispensing the medication kit(s) to the subject, site personnel will detach the outer part of the label(s) from the packaging and affix it to the source document.

During both the double-blind treatment as well as the open-label treatment period, one medication kit will be dispensed per visit by the IRT system. The medication is administered by the investigator or designated study staff at each visit.

#### **6.7.1 Handling of study treatment and additional treatment**

##### **6.7.1.1 Handling of study treatment**

Study treatment must be received by a designated person at the study site, handled and stored safely and properly and kept in a secured location to which only the investigator and designated site personnel have access. Upon receipt, all study treatment must be stored according to the instructions specified on the labels and in the Investigator's Brochure (IB). Clinical supplies are

to be dispensed only in accordance with the protocol. Technical complaints are to be reported to the respective Novartis Country Organization (CO) Quality Assurance.

Medication labels will be in the local language and comply with the legal requirements of each country. They will include storage conditions for the study treatment but no information about the subject except for the medication number.

The investigator must maintain an accurate record of the shipment and dispensing of study treatment in a drug accountability log. Monitoring of drug accountability will be performed by monitors during site visits or remotely and at the completion of the trial.

At the conclusion of the study, and as appropriate during the course of the study, the investigator will return all unused study treatment, packaging, drug labels, and a copy of the completed drug accountability log to the Novartis monitor or to the Novartis address provided in the investigator folder at each site.

#### **6.7.1.2 Handling of additional treatment**

Not applicable.

#### **6.7.2 Instruction for prescribing and taking study treatment**

Subcutaneous (s.c.) injections are to be administered in the clinic by qualified staff at drug dispensing visit.

For purposes of study treatment dosing, “q.m.” refers to an every 4 weeks injection regimen. The study drug administration date should be in 4-week increments ( $\pm$  5 days) from the first dose of study drug. Any dose administrations that may occur greater than  $\pm$  5 days from the 4-week timepoint (e.g. subject unavailability) should be discussed with the Sponsor prior to dosing. The anatomical sites for administration of investigational product are the upper arm, upper thigh, or abdomen; the location of the injection sites should be documented in the source document.

One injection will be administered by qualified study staff at each dosing visit during the 12-week treatment period (i.e. at Day 1 and Weeks 4 and 8). Subjects will be administered one of the following, depending on their randomization:

- 70 mg erenumab: one 70 mg erenumab syringe
- Placebo: one placebo syringe

One injection of 70 mg erenumab will be administered by qualified study staff at each visit during the open-label treatment period.

The investigator must promote compliance administering the study treatment exactly as prescribed. The investigational product dose is fixed and will not be adjusted for individual subjects during the study. There are no temporal restrictions for study drug administration (eg, proximity to meals, sleep or activity).

All kits of study treatment assigned will be recorded in the IRT, both for the double-blind treatment and the open-label treatment period. Novartis monitors will reconcile treatment assigned vs treatment administered and ensure that the information is congruent during their monitoring visits.

During the COVID-19 pandemic:

During the **COVID-19 pandemic** that limits or prevents on-site study visits, delivery of study drug directly to a subject's home is generally permitted in the event the Investigator has decided that an on-site visit by the subject is no longer appropriate or possible, and that it is in the interest of the subject's health to administer (e.g., self-injection or study staff administration at subjects' home) the study treatment even without performing an on-site visit. Implementation will need to be discussed with Novartis (see section 7 for required training process). The dispatch of study drug from the site to the subject's home remains under the accountability of the investigator. Each shipment/provisioning will be for a maximum of 1 month supply. In this case, regular phone calls or virtual contacts (at the time of every scheduled visit, or more frequently if needed) will occur between the site and the subject for instructional purposes, safety monitoring, and discussion of the subject's health status until the subjects can again visit the site.

